### B3. DESCRIPTION OF RESEARCH PROTOCOL

#### A. STUDY DESIGN – OVERVIEW, METHODS, PROCEDURES

##### Experimental design and methods

**Study Design**

Pragmatic prospective randomized controlled assessor-blinded effect-size finding trial at two academic tertiary care hospitals: Beth Israel Deaconess Medical Center (BIDMC) and Massachusetts General Hospital (MGH).

Prior to randomization, if subjects are eligible on the basis of inclusion and exclusion criteria, informed consent will be obtained from the participants. Once informed consent is obtained, patients will be randomized in a 1:1-ratio to one of two study arms: standard care non-depolarizing NMBA use (**C**) versus avoidance of non-depolarizing NMBA (**NR**) by computer-generated variable block size random allocation stratified a) study site (MGH or BIDMC) and b) expected preoperative risk of PPC (<40% and ≥40%) as predicted by expanded risk stratification tool as defined above (**Table 1**). Since blinding to use of NMBA is unfeasible, anesthesia team members would be aware of group assignment.

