### **Preliminary studies**

Our study is aimed at patients with high pre-test probability of developing PPCs. In order to identify such patients preoperatively we developed a risk prediction score (**Table 1**) using data from all patients who underwent non-cardiac procedures under general anesthesia with endotracheal intubation at MGH and BIDMC between 2007-2015. 12.2% patients developed PPC (defined as a composite of reintubation within 7 days and respiratory failure, respiratory infection, bronchospasm, atelectasis, pleural effusion, aspiration pneumonitis, pneumothorax within 28 days). Our risk prediction-model which we developed using our published standards demonstrates good discrimination (AUROC of 0.84). We plan to use this prediction instrument along with expanded definition of high risk surgical services as defined by well validated SPORC score (vascular,

transplant, neurosurgery, thoracic, general and burn surgery) and physician review of electronic health records to determine “high risk surgery” to screen for eligibility. **Table 2** shows the predicted incidence of PPC in different risk subgroups of patients (MGH and BIDMC) in an 18-month period.

Risk Prediction Score		Estimated Risk of outcome	
High-risk surgery*	13	Score Point Value	Probability of Outcome (%)
Inpatient surgery	11		
Pneumonia within 1 month	8	0	0.2
ASA $\geq 3$	3	5	0.9
Age $\geq 80$	2	10	3.5
Duration of surgery > 3 hours	2	15	12.3
History of heart failure within 1 year	2	20	35.4
Alcohol abuse within 1 year	1	25	68.2
Home oxygen therapy	1	30	89.3
BMI < 18.5 kg/m 	1	35	97.0
Chronic pulmonary disease within 1 year	1	40	99.2
Total points	44	44	99.8
*ENT, thoracic, vascular, transplant, neurosurgery, thoracic, general, and burn surgery			

\*The expanded definition of high risk surgical services as defined by SPORC score includes vascular, transplant, neurosurgery, thoracic, general and burn surgery.

**Table 1:** Risk prediction tool and estimated risk of outcomes. Logistic regression was used to build a model including all candidate predictors. Stepwise elimination was performed with a  $p = 0.01$  for retaining in the model. Individual weighting values were determined by dividing the respective beta coefficient by the overall smallest beta coefficient of all predictor variables. Rounded to the nearest integer, the score point values were multiplied by the corresponding predictors, thus estimating the final prediction instrument.

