## 2. SUBJECT SELECTION

### Inclusion criteria:

1. At least 18 years of age
2. Undergoing non-cardiac surgery under general anesthesia with an endotracheal tube
3. High estimated preoperative risk of PPC i.e. Score  $\geq 20$  based on combination of expanded risk prediction score (including high risk services as determined by SPORC scoring system) and physician review of electronic medical record (Table 1)

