### Exclusion criteria:

1. Emergency surgery
2. Ambulatory (outpatient) surgery
3. Scheduled for elective postoperative ventilation
4. Planned return to operating room within 7 days of index procedure
5. Exposure to general anesthesia within 7 days prior to planned procedure
6. Requirement mechanical ventilation at baseline (not including stable use of CPAP/BiPAP)
7. Pregnant patients: as detected by patient self-reporting or diagnosed by preoperative pregnancy testing according to institutional policies at BIDMC and MGH
8. Allergy to either non-depolarizing muscle relaxants or sugammadex

9. Clinician refusal
10. Prisoner

*Women of childbearing potential:*

Women of childbearing potential will be eligible for enrollment in this study. Preoperative pregnancy testing will take place according to the current BIDMC/MGH (as applicable) surgery and anesthesia guidelines. No additional serum or urine pregnancy test(s) will be performed for research purposes. Subjects will be excluded from participation if they are pregnant.

*Gender and Racial Distribution of Subjects:*

We anticipate that our study population will reflect the normal distribution of race and gender of patients presenting for non-cardiac surgeries at MGH and BIDMC

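### The 40% risk cut used to stratify randomisation sits just above the eligibility floor, so it balances little of the risk variation among eligible patients

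*Combined protocol and SAP*

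**What the plan says.** - **Allocation (B3.A, Study Design).** The plan states that "patients will be randomized in a 1:1-ratio to one of two study arms", using computer-generated variable blocks. The strata are site and "expected preoperative risk of PPC (<40% and ≥40%) as predicted by expanded risk stratification tool as defined above".
- **Eligibility (Section 2, Inclusion criteria).** The third criterion is "High estimated preoperative risk of PPC i.e. Score" of 20 or more, taken from the expanded tool together with physician review of the record.
- **Exclusions (Section 2).** The second is "Ambulatory (outpatient) surgery".
- **Risk tool (B2, Preliminary studies, Table 1).** The table gives points per predictor and, beside them, a column headed "Probability of Outcome" at selected scores.
- **Expected numbers (B2, Table 2).** Patients are counted by predicted-risk band over 18 months at the two hospitals.
- **Analysis (Section 1, Data Analysis).** The primary composite is compared by Chi-square or Fisher's exact test. A logistic regression relates it to treatment, with no covariates named. Adjustment for patient and procedural risk appears only in exploratory sensitivity analyses.

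No reason is given for choosing 40%.

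**The concern.** Stratifying on a prognostic score helps when the cut divides the enrolled patients into groups of useful size that differ in risk. Here the cut is made on a scale whose lower part has already been removed by the entry criterion. If nearly everyone falls on one side, the arms can differ by chance in score across almost the whole eligible range, and the list does little to prevent it. That matters in a trial of about 100 patients whose stated purpose is to find an effect size for a later study. It matters more when the primary test ignores the score as well.

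**Working it through.** **Inputs.** Score floor of 20 (Inclusion criteria). Table 1 probabilities, read from the last two entries of the rows "History of heart failure within 1 year 2 20 35.4" and "Alcohol abuse within 1 year 1 25 68.2": 35.4% at 20 points and 68.2% at 25. High-risk surgery 13 points, inpatient surgery 11 points (Table 1). Table 2 counts: 288 at 30% to under 40%, 215 at 40% to under 50%, 2,567 at 50% or more. At least 50 per arm (Section 1).

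**1. The plan's sample size.** For 40% versus 15%, two-sided 0.05, 80% power, the pooled formula is

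n = [1.960 × √(2 × 0.275 × 0.725) + 0.842 × √(0.40 × 0.60 + 0.15 × 0.85)]² / 0.25² = (1.238 + 0.510)² / 0.0625, about 49 per arm.

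The stated 50 is reproduced (power 80.9%), so 100 patients is the right base for what follows.

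**2. Risk at each score.** Table 1 is very nearly a straight line on the log-odds scale.

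- logit(0.354) = −0.602 and logit(0.682) = 0.763.
- Slope = (0.763 + 0.602) / 5 = 0.273 per point.

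| Score | Predicted risk |
|---|---|
| 19 | 29.4% |
| 20 | 35.4% (Table 1) |
| 21 | 41.9% |
| 22 | 48.6% |
| 23 | 55.4% |
| 24 | 62.0% |
| 25 | 68.2% (Table 1) |

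Among patients scoring 20 or more, only a score of exactly 20 lies below 40%. The upper stratum covers scores 21 to 44, about 42% to 99.8%.

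**3. Who can enter the lower stratum.** Outpatients are excluded, so every patient carries the 11 inpatient points. High-risk surgery brings the total to 11 + 13 = 24, about 62%. An inpatient having surgery on a listed service therefore cannot be in the lower stratum. It is open only to other inpatients with exactly 9 further points, for example pneumonia within a month (8) plus a single 1-point item.

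**4. Expected split.** A score of 19 is below 30% and a score of 21 is above 40%, so Table 2's band from 30% to under 40% corresponds to score 20 alone.

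- Patients at 30% or more: 288 + 215 + 2,567 = 3,070.
- Lower stratum: 288 / 3,070 = 9.4%. Upper stratum: 2,782 / 3,070 = 90.6%.
- In 100 patients: about 9 and 91, or 4 to 5 lower-stratum patients per site if the sites enrol equally.
- Scores 20 to 22 together: 503 / 3,070 = 16.4%. On these counts the median eligible score is 23 or higher, well above the cut.

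**5. Chance imbalance left in the upper stratum (illustration).** Assume, since the documents do not say, a score SD of 2 to 3 points and 45 patients per arm.

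- 95% range for the difference in mean score: ±1.96 × SD × √(2/45) = ±0.83 to ±1.24 points.
- As a baseline odds ratio: exp(0.273 × 0.83) = 1.25 to exp(0.273 × 1.24) = 1.40.

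This takes the Table 1 slope at face value within the eligible range.

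**The case against.** The strongest reply is that little is lost in practice. In a simulation of 100 patients (assumptions not in the documents: 9.4% at score 20, the rest spread over 21 to 30, the Table 1 slope, control incidence about 38%, true difference about 24 points), the results were:

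| | Site only | 40% cut | Near-median cut |
|---|---|---|---|
| SD of between-arm difference in mean score (points) | 0.56 | 0.48 | 0.33 |
| SD of estimated risk difference (percentage points) | not reported | 8.6 | 8.2 |
| Power, unadjusted test | not reported | 78.9% | 79.0% |
| Type I error | not reported | 4.8% | 4.7% |

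The values depend on the assumed spread of scores. They show that the present cut does some balancing, that a median cut does more, and that moving the cut alone barely changes the power of an unadjusted test. All of that stands, and it is why the fix includes the analysis.

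Four stronger readings might be inferred, and the documents do not support them.

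- **That the stratification balances nothing.** About 9 in 100 patients are allocated within their own stratum, and site stratification is unaffected.
- **That the lower stratum will be almost empty because most patients come from listed services.** No case mix by service is given. Table 2 is the only count, and it gives about 9%.
- **That the planned analysis of effect moderation by risk is disabled.** Section 1 names the preoperative risk score, not the stratum. The score varies among eligible patients wherever the cut is placed, and the analysis is labelled exploratory.
- **That the score is the strongest prognostic factor in this trial.** The AUROC of 0.84 comes from all non-cardiac patients, 78.2% of whom are below 10% risk in Table 2. It says little about discrimination among scores of 20 or more. The development composite also differs from the trial endpoint.

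**Conclusion.** The point holds as a matter of efficiency. By the protocol's own tables the lower risk stratum is one score value wide and holds about 9% of eligible patients. The other 91% or so, from about 42% to 99.8% predicted risk, are stratified by site only. The primary test as written makes no use of the score either. Allocation is still random and the comparison unbiased; what is lost is chance balance and some precision.

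The 9.4% is approximate in both directions. Table 2 precedes the exclusions and does not say which definition of high-risk surgery it uses. If physician review could admit patients whose calculated score is below 20, the lower stratum would be larger, although the Preliminary studies section ties that review to deciding what counts as high-risk surgery. The score of 21 falling above 40% rests on interpolation between two tabulated points, but Table 1 is so close to linear in log-odds that this is not in real doubt.

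Severity is minor to moderate: a cheap improvement worth making, not a defect that must be cured before the trial can be interpreted.

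**What to change.** **If randomisation has not started.** Take the 2007-2015 development data, keep elective inpatients scoring 20 or more, and find their median score. Scores are whole numbers, so choose the cut that divides them most evenly. State it in points rather than as a percentage, and regenerate the list with that cut and site.

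**In either case, and as the only change if randomisation has begun.** Prespecify the primary comparison as a logistic model with treatment, site and the continuous risk score. Report a marginal risk difference standardised over the trial population, or an odds ratio, and say in advance which is primary. Keep the Chi-square or Fisher test as the unadjusted supporting analysis. At the planned rates there would be about 0.40 × 50 + 0.15 × 50 = 27.5 events, enough for a model this small. If the list is already in use, leave it as it is.

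**Cost.** One query of data already held, a regenerated list where applicable, and a short amendment. No extra patients and no new data collection, since the score is calculated at screening. If the odds ratio is reported, it is conditional on site and score rather than marginal, which should be stated when it is carried into the design of the later trial.

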**Intervention:**

Pre- and intraoperative management plan would be left to the choice of the anesthetic team. The only protocolized restrictions in the two groups include the use or avoidance of non-depolarizing neuromuscular blocking agents. Normally, use or avoidance of non-depolarizing muscle relaxants for maintenance of general anesthesia is a clinical decision and either technique is accepted as standard of care at both participating centers. Choice and technique of induction and maintenance of anesthesia, use of vasopressors, perioperative antibiotics, analgesics/adjunct regional techniques, PONV prophylaxis, fluid and blood component therapy would be left at the discretion of the anesthesia team. Lung protective ventilatory strategies would be recommended. Use of monitors in addition to those recommended by standard ASA guidelines would be left to the discretion of the anesthesia team. Post anesthetic care and subsequent treatment would be left at the discretion of anesthesia and surgical teams per institutional protocols. Once a patient is enrolled into the study, the study team will review the protocol with the anesthesia care team before commencement of the surgery to address any questions or concerns.

[figure not shown]
**Control Group (C):** Use of neuromuscular monitoring would be allowed and management of neuromuscular blockade would be left at the discretion of the attending anesthesiologist. Endotracheal intubation would be facilitated by either Rocuronium ( $0.6\text{-}1\text{mg kg}^{-1}$ ) or Succinylcholine ( $1\text{-}1.5\text{mg kg}^{-1}$ ) and further dosing of Rocuronium would be left at the discretion of the anesthesia team members. Neuromuscular blockade would be reversed with either Sugammadex or Neostigmine (based on institutional availability) and trachea would be extubated once patient meets criteria per attending anesthesiologist.

**No Relaxant Group (NR):** Endotracheal intubation would be facilitated by Succinylcholine ( $1\text{-}1.5\text{mg/kg}$ ) or Remifentanyl ( $1\text{-}2\text{mcg kg}^{-1}$ ) if Succinylcholine use is contraindicated. Use of both Succinylcholine and Remifentanyl has been shown to provide excellent intubating conditions and is used commonly by practitioners. **No** non-depolarizing NMBA would be administered to the patients randomized to the **NR** group. Use of deeper plane of inhaled anesthetics or adjuncts (opioids, propofol, dexmedetomidine or ketamine) either as boluses or infusion would be recommended (**Figure 3**) in case of sustained high peak airway pressures ( $>35\text{mm Hg}$ ), high intra-abdominal pressure, involuntary patient/diaphragmatic movement hindering surgical exposure and dissection. Choice and dose of adjunct/s to optimize operating conditions would be left to the discretion of the anesthesia team.

**Use of rescue Neuromuscular blocking agents:**

In case of *sustained inability* to obtain optimal surgical conditions despite optimal use of adjuncts, patients would be allowed a **rescue dose** of  $0.2\text{mg kg}^{-1}$  of Rocuronium. Repeat dosages would be allowed only if sub-optimal operating conditions persist despite optimal use of adjunctive therapies.

In case of neuromuscular agent being used as rescue, NM blockade would be reversed at the conclusion of procedure with Sugammadex or Neostigmine (based on institutional availability) and trachea would be extubated once the patient meets subjective criterion including (TOF%>0.9) using quantitative monitoring.

**Figure 3:** Suggested algorithm to mitigate inadequate operating conditions in NR arm

### Study Endpoints:

1. Primary Endpoint: Composite of postoperative pulmonary complications (respiratory failure, suspected respiratory infection, aspiration pneumonia or pneumonitis, atelectasis, bronchospasm and reintubation) and all cause in-hospital mortality both within 28 days of index operative procedure
2. Secondary endpoint (safety):
  - a. Vasopressor use between groups,
  - b. Duration of intraoperative hypotension (defined as mean arterial pressure <55mmHg),
  - c. Surgeon's assessment of surgical field.
3. Other end points:
  - a. Time to post-anesthesia care unit (PACU) discharge readiness,
  - b. Cost of anesthetic medication,
  - c. Rate of unplanned ICU admission or return to operating room within 24 hours,
  - d. Hospital length of stay
  - e. 30-day readmission rates.

The following baseline variables will also be collected: Clinical and demographic variables will be collected including age, gender, body mass index, type and severity of chronic lung disease, ASA class, obstructive sleep apnea, use of CPAP/Bipap, smoking history, hypertension, coronary artery disease, heart failure, cerebrovascular accident or neurologic dysfunction, history of aspiration, use of home oxygen, chronic kidney disease, diabetes mellitus, Charlson comorbidity index and Procedural Severity Score. Additionally, to track other important intraoperative and postoperative

factors related to overall patient outcome and protocol adherence, we will record administrative, demographic, clinical and billing data including:

- Vital Signs
- Medications administered
- Ventilator settings
- Urine output
- End tidal carbon dioxide concentration
- Dead space ventilation
- Alveolar-Arterial oxygen gradient
- Blood transfusion history
- Length of operation
- Type of operation

*Assessment of Primary Outcome:*

Detection of postoperative pulmonary complications and in-hospital mortality would be achieved by close review of the patient's medical records during the hospital stay, for a maximum of 28 days. Study team members blinded to the treatment assignment will review clinician/ nursing/ respiratory therapy notes, laboratory/ imaging data and communicate with the clinical team as needed. Attending surgeons would be asked to rate overall operating conditions at the end of the procedure on a numerical scale modified from an earlier study. To ensure blinding of assessors, printed anesthetic records will be placed in a sealed envelope and attached to the patient's chart after formal hand-off to nursing staff. Members of the clinical team will continue to have access to the anesthesia record through the electronic health record without restriction for the provision of clinical care.

*Adverse Event Reporting:*

We will assess for adverse events during the intraoperative period, as well as for the first 48 hours post-surgery.

Patients in this study are being randomized to anesthetic protocols that are both considered within the standard of care. We will adhere to the CCI post approval reporting requirements with regard to Adverse Events that are related, serious, and unexpected.

We will track the following pre-specified events as part of clinical outcome assessment. If any are deemed possibly related to study participation, they will be reported to the IRB in accordance with the reporting guidelines.

- Significant intraoperative hypoxemia
- Severe patient ventilator dyssynchrony
- Inability to ventilate
- Pneumothorax

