### B1. PURPOSE OF PROTOCOL

The purpose of the protocol is to test the hypothesis that elimination of the use of non-depolarizing neuromuscular blocking agents (NMBA) for maintenance of general anesthesia in patients at high risk of developing postoperative pulmonary complications (PPCs) undergoing non-cardiac operations is associated with reduced risk of PPCs.

*Specific Aim 1:* To test the primary hypothesis that avoidance of non-depolarizing NMBAs, as compared to standard care which includes the use of non-depolarizing NMBAs, is associated with a lower risk of a composite of PPCs (including respiratory failure, suspected respiratory infection, aspiration pneumonia or pneumonitis, atelectasis, bronchospasm and reintubation within 28 days of index operative procedure) and all cause in-hospital mortality both within 28 days of index operative procedure.

*Specific Aim 2:* To test the key-secondary hypothesis that avoidance of non-depolarizing NMBA, compared to standard care which includes the use of non-depolarizing NMBA, is associated with higher vasopressor equivalent dose, which may be the consequence of higher dosing of opioids and anesthetics. Further, we shall also evaluate the following secondary endpoints: duration of intraoperative hypotension (defined as mean arterial pressure <55mmHg), surgeon's assessment of surgical field, cost of anesthetic medications, time to PACU discharge readiness (interval between arrival and time when meeting PACU discharge criteria), rate of unplanned ICU admissions or return to operating room within 24 hours, hospital length of stay and 30-day readmission rates.

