#### **Importance:**

The need for safe anesthesia practices is growing in parallel with global surgical volume. Non-depolarizing NMBA are commonly used as part of 'balanced anesthesia techniques'. Though helpful in facilitating endotracheal intubation and optimizing surgical conditions, their use has been strongly associated with higher risk of postoperative complications. Large retrospective registry studies have consistently shown non-depolarizing NMBA use to be associated with increased risk of PPCs, hospital length of stay, overall costs and 30 day unplanned readmission rates. Overall, this may translate not only into significant *potentially avoidable* patient morbidity but also in substantial healthcare expenditure considering their widespread use.

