**Collaboration with MGH**

This randomized control trial is planned in collaboration with MGH. We plan to recruit patients in parallel at the two institutions (BIDMC and MGH) and implement the study protocol after obtaining institutional approval. [name] [name] shall be the site PI at MGH and work in collaboration with [name], PI at BIDMC. A research coordinator credentialed at MGH will work under the guidance of [name] to follow study protocol at MGH. Similarly, a study coordinator will work with [name] to follow protocol at BIDMC. Postoperative follow-up will be conducted by research staff credentialed at respective institutions through review of electronic medical records and in-person patient visits as appropriate for ascertaining components of PPC. Please see section B9 for more details on the collaboration.

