## 1. STATISTICAL CONSIDERATIONS

- a. **Sample Size Justification:** Assuming the incidence of PPC to be 40% and 15% in Groups C and NR, respectively, we estimated that we would need at least 50 patients in each group to achieve a two-sided  $\alpha = 0.05$  and 80% power. Although the effect size in this assumption is high, if a difference of this magnitude is observed, the study will be well-powered. However, due to the scant knowledge about the directionality of the effect that we are exploring, observing even a smaller difference in this preliminary study will be useful in estimating a reliable effect size that can be used in designing a larger, more definitive study in the future. Results from our secondary endpoints will provide valuable exploratory data on the safety and efficacy of maintenance of general anesthesia without non-depolarizing NMBA.
- b. **Data Analysis:** Descriptive statistics will be assessed and presented as mean( $\pm$ -SD), median(IQR) or frequencies and proportion depending on type and distribution. Differences between groups in continuous variables will be compared using parametric or non-parametric tests as appropriate. Categorical data including the primary outcome (composite of PPC and all cause 28 day in-hospital mortality) will be compared with Chi-square or Fisher's exact test as appropriate. Two-sided p-value of less than 0.05 will be considered significant for all analyses. Logistic regression will be used to assess the relationship between the composite outcome and use or avoidance of non-depolarizing NMBA. Data will be presented as odds ratio and 95% confidence intervals. Individual outcomes will be reported to demonstrate potential trends between the two groups. Continuous outcome variables will be compared between treatment groups using t-test or Wilcoxon rank sum test as appropriate. Exploratory sensitivity analyses will be conducted to analyze if treatment effects were moderated by study site, surgical site or preoperative risk score after adjusting for patient and procedural risk factors such as Charlson comorbidity index and Procedural Severity Score. Statistical consultation shall be provided by [name], PhD at MGH. Statisticians will be blinded to group assignment.

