#### **B4. POSSIBLE BENEFITS**

As this is a pilot study, it is not possible to predict whether there will be direct benefit to the individual subject. However, based on our review of the literature, it seems plausible that elimination of the use of non-depolarizing muscle relaxants could result in lower incidence of postoperative pulmonary complications. These could potentially translate to lower morbidity, mortality, hospital length of stay and lower unplanned ICU admissions. Additionally, results from this trial would compare the relative safety and efficacy of these two techniques.

Data from this study can potentially provide pilot data to design a larger more definitive multicenter trial to assess whether the elimination of routine use of neuromuscular blockers can improve patient outcomes.

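### PPCs are counted to day 28, but the stated detection method covers the hospital stay, so PPCs arising after discharge may be missed and the comparison can favour the arm discharged earlier

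*Combined protocol and SAP*

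**What the plan says.** Specific Aim 1 (B1) lists the PPC components, ending with "reintubation within 28 days of index operative procedure". The Study Endpoints list in B3 adds "all cause in-hospital mortality both within 28 days of index operative procedure" and applies the same window to the PPCs. In both places the in-hospital restriction is attached to death and not to the PPC components.

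The Assessment of Primary Outcome paragraph, directly after the endpoint list, says how events are found: blinded study staff review "medical records during the hospital stay, for a maximum of 28 days". Here the 28 days is an upper limit on the stay that is reviewed.

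Two other places bear on follow-up:

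- Collaboration with MGH describes postoperative follow-up by "review of electronic medical records and in-person patient visits as appropriate for ascertaining components of PPC". It mentions neither discharge nor day 28.
- "30-day readmission rates" appear among the other endpoints, with no link to PPC detection and no statement of how readmissions are found.

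Statistical Considerations compares the binary composite by chi-square or Fisher's exact test, with logistic regression for the odds ratio. Nothing there allows for unequal observation time.

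**The concern.** The definition and the detection rule select different events. Take a patient discharged on day 5 who returns with pneumonia on day 10. Under the endpoint definition this is an event. Under the detection paragraph an assessor could reasonably stop at discharge and record none. Two assessors following different paragraphs could code the same patient differently.

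Two consequences follow. If events are missed at the same rate in both arms, the observed rates shrink and power is lost. If one arm's event-free patients leave earlier, that arm is watched for less time and can show fewer PPCs without having fewer. Blinded assessment does not protect against this, because the assessor cannot judge records that are not opened. Discharge is not standardised either: the anesthesia team knows the assignment and postoperative care is left to the treating teams.

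The plan intends to use even a smaller observed difference to design a larger trial, so a bias of a few points would be carried forward.

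**Working it through.** **The plan's own figure.** Inputs from Statistical Considerations: "Assuming the incidence of PPC to be 40% and 15% in Groups C and NR, respectively", two-sided α = 0.05, 80% power, at least 50 per group. With pooled variance and mean rate 0.275:

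n = [1.96·√(2·0.275·0.725) + 0.8416·√(0.40·0.60 + 0.15·0.85)]² / 0.25² = (1.2377 + 0.5102)² / 0.0625 ≈ 48.9, so 49 per group.

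The stated 50 is reproduced. At 50 per group, power is 80.9% by the normal approximation and 81.9% by exact enumeration of the uncorrected chi-square test. The sample size is not in error, provided all 28-day events are found.

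**Equal loss in both arms.** Observed risk = true risk × (1 − share missed). The missed shares are assumptions.

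| Share missed | Observed C vs NR | Exact chi-square power, 50 per arm |
|---|---|---|
| 0% | 40% vs 15% | 81.9% |
| 5% | 38% vs 14.25% | 79.1% |
| 10% | 36% vs 13.5% | 76.1% |
| 20% | 32% vs 12% | 69.6% |

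Equal loss creates no difference when there is no true effect.

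**Unequal loss with no true effect.** Assume a true 28-day risk of 40% in both arms.

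| Missed in C / NR | Observed C vs NR | Odds ratio | Rejection rate |
|---|---|---|---|
| 0% / 0% | 40% vs 40% | 1.00 | 5.2% |
| 5% / 10% | 38% vs 36% | 0.92 | 5.5% |
| 10% / 20% | 36% vs 32% | 0.84 | 6.9% |
| 10% / 30% | 36% vs 28% | 0.69 | 13.5% |
| 20% / 10% | 32% vs 36% | 1.20 | 6.9% |

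The last row shows the bias reversing when the control arm misses more.

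**From stay to missed share.** Let onset be exponential with mean m days, truncated at day 28. The share captured by a discharge on day t is F(t) = (1 − e^(−t/m)) / (1 − e^(−28/m)). The spurious difference is 40 × [F(stay in C) − F(stay in NR)] points. Both m and the stays are assumptions.

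| Mean onset m | 6 vs 5 days | 6 vs 4 days |
|---|---|---|
| 1 day | 0.2 | 0.6 |
| 2 days | 1.3 | 3.4 |
| 3 days | 2.1 | 5.1 |
| 5 days | 2.7 | 5.9 |
| 8 days | 2.6 | 5.5 |

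For example, with m = 5 and stays of 6 vs 4 days, F is 0.701 and 0.553, giving 40 × 0.148 ≈ 5.9 points. That upper end requires about 30% and 45% of first PPCs to arise after discharge. If none do, the bias is zero.

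The model gives every patient in an arm the same discharge day. In practice only the discharge timing of patients still free of a PPC matters. A stay prolonged by an in-hospital PPC adds observation for someone already counted.

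**The case against.** The strongest reply is that the plan may already reach past discharge. The Collaboration with MGH paragraph has no stop at discharge, and the detection paragraph does not say index stay, so a readmission is not expressly excluded. This stands in part. It means that exclusive in-hospital ascertainment cannot be asserted. It does not supply a day-28 review, because follow-up as appropriate sets no time point and readmission is a separate endpoint.

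A reader might go further and infer that the no-relaxant arm will appear to have fewer PPCs because it is expected to go home earlier. The documents do not support that. Length of stay is listed as an endpoint with no predicted difference. The background section (Importance) reports only observational associations of relaxant use with "hospital length of stay, overall costs and 30 day unplanned readmission rates". B4 says of a lower PPC incidence: "These could potentially translate to lower morbidity, mortality, hospital length of stay and lower unplanned ICU admissions". In that account the shorter stay follows from fewer PPCs, so it gives no reason for event-free patients to leave earlier when there is no PPC effect. Statistical Considerations concedes that little is known about the direction of effect.

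The size is also open to challenge. The proposed mechanism, residual blockade after extubation, plausibly acts early. With an assumed mean onset of 1 to 2 days, the spurious difference is only 0.2 to 3.4 points. With stays of 6 vs 5 days, even a mean onset of 4 to 8 days raises the false-positive rate only from 5.2% to 5.9–6.4%. Finally, this is a pilot. These arguments limit the size and severity, but they do not remove the conflict between the definition and the detection rule.

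**Conclusion.** The concern holds as a conflict between a stated detection rule and the endpoint definition, with a possible bias whose size the documents do not fix. PPCs first arising after discharge fall within the endpoint but may not be detected. The comparison can then favour the arm discharged earlier. This needs two conditions: some first PPCs after discharge, and a difference between arms in discharge timing among event-free patients. The documents quantify neither.

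Over the assumed ranges (40% true risk in both arms, mean onset 1 to 8 days, stays differing by 1 to 2 days) the spurious difference is about 0.2 to 6 points against a planned 25. The loss of power needs no difference between arms: missing even 5% of events takes exact chi-square power just below the stated 80%. Because the trial's purpose is to find an effect size, this should be fixed, although it does not invalidate the design or the sample size.

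**What to change.** Amend the Assessment of Primary Outcome paragraph so that:

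- blinded record review runs to day 28 after the index procedure for every patient in both arms, whatever the discharge date;
- PPCs found in readmission, emergency and clinic records available at the enrolling hospital count toward the endpoint;
- the mortality component stays as in-hospital death by day 28, including death during a readmission. Counting deaths outside hospital would change the endpoint;
- the composite restricted to the index stay is reported as a sensitivity analysis.

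The Collaboration with MGH paragraph should refer to the same rule.

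Redefining the endpoint as in-hospital PPC up to day 28 would also remove the contradiction, but it keeps the unequal observation time and departs from Specific Aim 1.

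The cost is a wording change and modest extra chart review. The documents do not say how readmissions are found, so it should not be assumed that these records are already being opened. Events treated at other hospitals would still be missed, and the report should say so.
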